#### 8.4.2 Method of Detecting AEs, SAEs, and Other Reportable Safety Events

Care will be taken not to introduce bias when detecting AE and/or SAE and other reportable safety events. Open-ended and nonleading verbal questioning of the participant is the preferred method to inquire about AE occurrence.

#### 8.4.3 Follow-up of AE, SAE and Other Reportable Safety Event Information

After the initial AE/SAE report, the investigator is required to proactively follow each participant at subsequent visits/contacts. All AE, SAE, and other reportable safety events including pregnancy and exposure during breastfeeding, events of clinical interest (ECIs), Cancer and Overdose will be followed until resolution, stabilization, until the event is otherwise explained, or the participant is lost to follow-up (as defined in Section 7.3). In addition, the investigator will make every attempt to follow all nonserious AEs that occur in randomized participants for outcome. Further information on follow-up procedures is given in Appendix 4.

#### 8.4.4 Regulatory Reporting Requirements for SAE

- Prompt notification (within 24 hours) by the investigator to the Sponsor of SAE is essential so that legal obligations and ethical responsibilities towards the safety of participants and the safety of a study treatment under clinical investigation are met.
- The Sponsor has a legal responsibility to notify both the local regulatory authority and other regulatory agencies about the safety of a study treatment under clinical investigation. All AEs will be reported to regulatory authorities, IRB/IECs and investigators in accordance with all applicable global laws and regulations, ie, per ICH Topic E6 (R2) Guidelines for GCP.

- Investigator safety reports must be prepared for suspected unexpected serious adverse reactions (SUSARs) according to local regulatory requirements and Sponsor policy and forwarded to investigators as necessary.
- An investigator who receives an investigator safety report describing an SAE or other specific safety information (eg, summary or listing of SAE) from the Sponsor will file it along with the IB and will notify the IRB/IEC, if appropriate according to local requirements.

#### **8.4.5 Disease-related Events and/or Disease-related Outcomes Not Qualifying as AEs or SAEs**

Efficacy endpoints as outlined in this section will not be reported to the Sponsor as described in Section 8.4.1. Specifically, the suspected/actual events covered in this exception include any event that is disease progression/recurrence of the cancer under study.

The Sponsor will monitor unblinded aggregated efficacy endpoint events and safety data to ensure the safety of the participants in the study. Any suspected endpoint which upon review is not progression of the cancer under study will be forwarded to Global Pharmacovigilance as an SAE within 24 hours of determination that the event is not progression/not recurrence of the cancer under study.

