Participants whose treatment assignment has been unblinded by the investigator/delegate and/or nonstudy treating physician should continue to be monitored. Participants who qualify for Part 2 per the eligibility criteria in Section 6.7 may continue on the study.

The process for nonemergent unblinding at the time of disease recurrence in Part 1 requires the investigator to submit a Sponsor consultation form to the study clinical team requesting authorization for official unblinding upon disease recurrence and consideration to proceed into Part 2 of the study (Crossover/Rechallenge treatment). After unblinding is complete, the site will assess the participant's eligibility for Part 2 of the study and notify the Sponsor prior to beginning Part 2. The entry criteria for Part 2 are detailed in Section 6.7.

During the study, all data should be entered as soon as possible after a protocol visit or procedure is conducted. Upon first recurrence, every effort must be made to have all pending data entered into the eCRFs within 1 business day or before the site is unblinded to the

participant's treatment assignment. The site should ensure data for disease recurrence is entered in the database prior to unblinding. Additionally, any AEs and/or SAEs should be reported and causality attributed in the database prior to unblinding.

The study will be considered unblinded once the RFS endpoint has been achieved and has been reviewed by the eDMC. The Sponsor will identify to the sites the specific unblinding procedures to be followed.

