## **9.2 Responsibility for Analyses/In-house Blinding**

The statistical analysis of the data obtained from this study will be the responsibility of the Clinical Biostatistics Department of the Sponsor.

The Sponsor will generate the randomized allocation schedule(s) for study treatment assignment for this protocol, and the randomization will be implemented in IRT.

Part 1 of this study will be conducted as a double-blind study under in-house blinding procedures. Blinded Sponsor personnel will remain blinded throughout study conduct and the official, final database will not be unblinded until medical/scientific review has been performed, protocol deviations have been identified, and data have been declared final and complete. In addition, the site radiologist(s) will perform the imaging review without knowledge of treatment group assignment and provide their results to the site investigator.

Blinding with respect to planned efficacy interim analyses is described in Section 9.7 – Interim Analyses. Protocol-specified blinding to treatment assignment will be maintained at all investigational sites.

Part 2 of this study is open-label, so individuals participating in Part 2 will not remain blinded throughout the entire conduct of the study.

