### **9.7.2 Efficacy Interim Analyses**

There are 5 efficacy interim analyses and a final analysis planned for this study (see [Table 11](#)). Details on how the planned analyses are incorporated into establishing statistical significance and the boundaries with regard to efficacy are discussed further in Section 9.8, Multiplicity.

Treatment level results of the efficacy interim analyses will be provided by an external unblinded statistician to the eDMC.

The eDMC will serve as the primary reviewer of the results of the interim analyses and will make recommendations for discontinuation of the study or modification to an Executive Oversight Committee (EOC) of the Sponsor. Depending on the recommendation of the eDMC, the Sponsor may prepare a regulatory submission. Participant-level unblinding to support regulatory filing will be restricted to a designate team at the Sponsor, who will have no other responsibilities associated with the study.

If the eDMC recommends modifications to the design of the protocol or discontinuation of the study, this EOC may be unblinded to study results at the treatment level in order to act on these recommendations or facilitate regulatory filing. Limited additional Sponsor personnel may also be unblinded to the treatment level results of the IA(s), if required, in order to act on the recommendations of the eDMC or facilitate regulatory filing. The extent to which individuals are unblinded with respect to results of interim analyses will be documented. Additional logistical details, revisions to the above plan and data monitoring guidance will be provided in the eDMC Charter.

Prior to final study unblinding, the external unblinded statistician will not be involved in any discussions regarding modifications to the protocol, statistical methods, identification of protocol deviations, or data validation efforts after the interim analyses.

Table 11 Analyses Planned, Endpoints Evaluated, and Drivers of Timing

Analysis	Endpoint	Criteria for Conduct of Analysis	Estimated Time after First Participant Randomized	Primary Purpose of Analysis
IA 1: Interim RFS analysis	RFS	(1) enrollment is completed, and (2) ~ 128 RFS events observed	~33 months	RFS IA
IA 2: Final RFS analysis	RFS	~179 RFS events observed	~48 months	RFS FA
IA 3: Interim DMFS analysis	DMFS	~146 DMFS events observed	~60 months	DMFS IA
IA 4: Final DMFS analysis;	DMFS	~195 DMFS events	~108 months	DMFS FA
IA 5: Interim OS analysis	OS	~154 OS events	~120 months	OS IA

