3.2 Responsibility for Analyses/In-House Blinding

The statistical analysis of the data obtained from this study will be the responsibility of the Clinical Biostatistics Department of the Sponsor.

The Sponsor will generate the randomized allocation schedule(s) for study treatment assignment for this protocol, and the randomization will be implemented in IRT.

Part 1 of this trial will be conducted as a double-blind trial under in-house blinding procedures. Blinded sponsor personnel will remain blinded throughout study conduct and the official, final database will not be unblinded until medical/scientific review has been performed, protocol deviations have been identified, and data have been declared final and complete. In addition, the site radiologist(s) will perform the imaging review without knowledge of treatment group assignment and provide their results to the site investigator.

Blinding with respect to planned efficacy interim analyses is described in Section 3.7 – Interim Analyses. Protocol-specified blinding to treatment assignment will be maintained at all investigational sites.

Part 2 of this trial is open-label, so individuals participating in Part 2 will not remain blinded throughout the entire conduct of the trial.

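### Protocol 8.4.5 has the Sponsor monitor unblinded aggregated recurrence events without limit, which does not fit Part 1 in-house blinding or the eDMC's role before RFS is decided

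*Protocol*

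**What the plan says.** **The sentence at issue.** Protocol 8.4.5 takes recurrence and progression of the melanoma out of adverse event reporting and then says: "The Sponsor will monitor unblinded aggregated efficacy endpoint events and safety data to ensure the safety of the participants in the study". The next sentence gives a case-level task: "Any suspected endpoint which upon review is not progression of the cancer under study will be forwarded to Global Pharmacovigilance as an SAE", with a 24-hour limit.

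**Blinding.** Protocol 9.2: "Part 1 of this study will be conducted as a double-blind study under in-house blinding procedures", and "Blinded Sponsor personnel will remain blinded throughout study conduct". SAP 3.2 repeats this: "Part 1 of this trial will be conducted as a double-blind trial under in-house blinding procedures".

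**Route for treatment-level results.** Protocol 9.7.2: "Treatment level results of the efficacy interim analyses will be provided by an external unblinded statistician to the eDMC". SAP 3.7 agrees. If the eDMC recommends changing or stopping the study, the Executive Oversight Committee (EOC) may be unblinded at treatment level. In addition, "Limited additional Sponsor personnel may also be unblinded to the treatment level results of the IA(s), if required", for the same purposes. A separate Sponsor team may be unblinded at participant level for a regulatory filing, and it may have no other duties on the study.

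**Safety oversight.** Protocol 9.7.1 and SAP 3.7.2 give regular safety monitoring to the eDMC. Protocol 9.8.4 and SAP 3.8.4 make it responsible for overall risk/benefit and let it ask for efficacy data when a safety concern arises. If it does, an RFS sensitivity analysis with a conservative multiplicity adjustment follows. Protocol 10.1.4.3 has the eDMC monitor interim data in addition to routine study monitoring.

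**Disclosure after recurrence.** Under Protocol 8.1.11, once a participant has a first recurrence, Sponsor staff other than the blinded statisticians may learn that participant's assignment, for follow-up care. The same section fixes when the blind ends: "The study will be considered unblinded once the RFS endpoint has been achieved and has been reviewed by the eDMC". Part 2 is open-label (Protocol 6.9 and 9.2).

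**The concern.** Recurrence is a component of RFS, the single primary endpoint. Read literally, 8.4.5 lets the Sponsor keep an unblinded running view of those events while Part 1 is still double-blind. The protocol elsewhere keeps Part 1 blinded in-house and hands unblinded efficacy review to an external committee.

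At stake is operational bias. People who design amendments, query data or manage sites could do so with knowledge of how the arms compare, and the Sponsor would find it harder to show that mid-trial decisions were independent of results. The plan takes unplanned efficacy looks seriously when the eDMC makes them, since it attaches a sensitivity analysis for RFS. It has no counterpart for a look by the Sponsor.

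**Working it through.** The point turns on text, so the check sets the passages side by side.

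**1. Which events?** Section 8.4.5 covers recurrence and progression of the cancer under study. Protocol 9.4.1.1 defines RFS as time to recurrence at any site or death. The monitored events therefore include the recurrence part of the primary endpoint.

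**2. What limits?** Section 8.4.5 names no study part, no period, no team and no firewall.

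**3. How does each rule compare?**

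| Rule | What it covers | Against 8.4.5, Part 1, before RFS is decided |
|---|---|---|
| In-house blinding (Protocol 9.2, SAP 3.2) | Part 1 conduct; blinded Sponsor personnel stay blinded | Inconsistent, unless a separate unblinded Sponsor group exists |
| eDMC responsibility for risk/benefit and safety-prompted efficacy review (Protocol 9.8.4, SAP 3.8.4) | The same safety purpose that 8.4.5 gives | Inconsistent: 8.4.5 assigns an unblinded efficacy review for safety to the Sponsor |
| External statistician to eDMC (Protocol 9.7.2, SAP 3.7) | Results of the efficacy interim analyses | 8.4.5 lies outside this route, but the text does not expressly cover routine monitoring |
| Disclosure after recurrence (Protocol 8.1.11) | One participant at a time, for care; statisticians excluded | Does not authorize an aggregate review |
| Part 2 open-label (Protocol 6.9, 9.2) | Part 2 | No conflict |

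**4. Is there an unblinded Sponsor group?** The phrase about blinded personnel in 9.2 leaves room for one. Section 8.4.5 names none. The one separated Sponsor team, in 9.7.2, is for regulatory filing and may have no other responsibilities on the study, so it cannot do this monitoring.

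**5. What if *aggregated* means pooled?** A display pooled over arms shows totals only and is a blinded display. The word *unblinded* is then wrong. If the display is by arm, the sentence conflicts with the first two rows of the table. It needs correcting on either reading.

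**6. How long is the period?** It runs from first randomization to IA1 (about 128 RFS events, month 33) or IA2 (about 179 events, month 48), from Protocol Table 11. Two RFS looks are planned in that time, both through the eDMC.

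**7. Does any design figure move?** Inputs: 128 and 179 events, HR 0.60, one-sided alpha 0.025, Lan-DeMets O'Brien-Fleming spending (Protocol 9.8.1 and 9.9.1).

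- Information fraction at IA1: 128/179 = 0.715.
- Alpha spent at IA1: 2[1 − Φ(2.2414/√0.715)] = 0.0080, giving Z = 2.407 (plan 2.4115). The final Z is 2.003 (plan 2.0029).
- Power ignoring the interim look: Φ(0.5108 × √179/2 − 1.960) = Φ(1.457) = 0.927.
- Two-look power: 0.924 (plan 0.9190).

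The plan's figures reproduce closely. Who may see the data is not an input to any of them, so none changes.

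**The case against.** The strongest reply is that the protocol already lets by-arm knowledge arise inside the Sponsor. All participants are unblinded at recurrence, the Sponsor's clinical team authorizes each unblinding, and staff other than the blinded statisticians may then know the assignment. This stands as a limit on the point. A reader might infer that 8.4.5 is the sole leak and that rewording it closes the gap. The documents do not support that. What 8.4.5 adds is apparent authority for an aggregate unblinded review, which 8.1.11 does not give. This is also why a change to 8.1.11 belongs in the fix.

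Three textual replies also stand in part:

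- Section 9.2 binds blinded Sponsor personnel, not every Sponsor employee. That leaves room for another group, but none is named.
- Section 9.7.2 speaks only of results of the efficacy interim analyses. A reader might infer that the plan makes all treatment-level data exclusive to the eDMC. It does not: the EOC and limited staff may see interim results on stated conditions, and routine safety monitoring is not mentioned there.
- Section 10.1.4.3 has the eDMC supplement routine monitoring, and 8.4.4 gives the Sponsor its own legal safety-reporting duty. Sponsor safety monitoring is therefore legitimate. Neither section says it may use unblinded aggregate efficacy data, and 9.8.4 places that review with the eDMC.

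Finally, *unblinded* may be a drafting slip for *blinded*. That is possible, and it would make the harm hypothetical. The sentence would still instruct the wrong thing.

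**Conclusion.** The sentence in 8.4.5 is wrong as written. For Part 1, until RFS has been achieved and reviewed by the eDMC, it is inconsistent with in-house blinding and with the eDMC's assigned review role, and it lies outside the only described route for treatment-level efficacy results. The open-label Part 2 and the period after that review are not affected.

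The exposure lasts up to about 33 or 48 months, and the consequence is a risk of operational bias. A reader might go further and infer an inflated type I error, or that a by-arm count would give away the RFS result. The documents support neither. Alpha, boundaries and power are unchanged, 8.4.5 does not say that its display is split by arm, and nothing shows that any such review took place.

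Confidence is moderate. The eDMC Charter and the Procedure Manual were not provided; either may name a firewalled group or restrict the use of disclosed assignments. Even so, the protocol should not contradict itself.

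**What to change.** Replace the sentence in 8.4.5 with:

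> For Part 1, until the RFS endpoint has been achieved and reviewed by the eDMC (Section 8.1.11) or the final RFS analysis has been completed, the Sponsor will monitor aggregated efficacy endpoint events and safety data pooled across treatment arms. Aggregate review by treatment arm is done by the eDMC (Sections 9.7.1, 9.8.4 and 10.1.4.3), supported by the external unblinded statistician; Sponsor access to treatment-level efficacy results is only as Section 9.7.2 allows.

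The reference to the final RFS analysis is needed because the condition in 8.1.11 would never be met if RFS failed at IA2. Section 9.7.2 is cited for efficacy results only, since it does not govern safety data.

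Add to 8.1.11, as a required part of the change:

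> Assignments disclosed after recurrence are used for that participant's care and Part 2 eligibility and are not compiled by treatment arm by the Sponsor study team during that period.

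Leave unchanged the Sponsor's case-level review and SAE forwarding in 8.4.5, its regulatory reporting under 8.4.4, the sensitivity analysis in 9.8.4, and Part 2. Check that the eDMC Charter and Procedure Manual agree.

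The cost is one replaced sentence, one added sentence and that check. Participants, visits, analyses, alpha and power stay as they are. The drawback is that, until RFS is decided, the Sponsor relies on the eDMC for signals by arm, which the safety oversight sections largely plan for already.

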#### **8.4.6 Pregnancy and Exposure During Breastfeeding**

Although pregnancy and infant exposure during breastfeeding are not considered AEs, any pregnancy or infant exposure during breastfeeding in a participant (spontaneously reported to the investigator or their designee) that occurs during the study are reportable to the Sponsor.

All reported pregnancies must be followed to the completion/termination of the pregnancy. Pregnancy outcomes of spontaneous abortion, missed abortion, benign hydatidiform mole, blighted ovum, fetal death, intrauterine death, miscarriage and stillbirth must be reported as serious events (Important Medical Events). If the pregnancy continues to term, the outcome (health of infant) must also be reported.

#### **8.4.7 Events of Clinical Interest (ECIs)**

Selected nonserious and serious adverse events are also known as ECIs and must be reported to the Sponsor.

Events of clinical interest for this study include:

1. an overdose of Sponsor's product, as defined in Section 8.5, that is not associated with clinical symptoms or abnormal laboratory results.
2. an elevated AST or ALT lab value that is greater than or equal to 3X the upper limit of normal and an elevated total bilirubin lab value that is greater than or equal to 2X the upper limit of normal and, at the same time, an alkaline phosphatase lab value that is less than 2X the upper limit of normal, as determined by way of protocol-specified laboratory testing or unscheduled laboratory testing.\*

- \* Note: These criteria are based upon available regulatory guidance documents. The purpose of the criteria is to specify a threshold of abnormal hepatic tests that may require an additional evaluation for an underlying etiology. The study site guidance for assessment and follow-up of these criteria can be found in the Investigator Trial File Binder (or equivalent).

## **8.5 Treatment of Overdose**

For this study, an overdose of pembrolizumab will be defined as any dose of 1000 mg or greater, or  $\geq 5$  times the indicated dose.

No specific information is available on the treatment of overdose of pembrolizumab. In the event of overdose, the participant should be observed closely for signs of toxicity. Appropriate supportive treatment should be provided if clinically indicated.

Decisions regarding dose interruptions or modifications will be made by the investigator in consultation with the Sponsor based on the clinical evaluation of the participant.

## **8.6 Pharmacokinetics**

To evaluate the immunogenicity and exposure of pembrolizumab in this indication in pediatric participants in Part I of this study, sample collections for analysis of PK and ADA are currently planned as shown in the SoA (Section 1.3.1). Blood samples for PK and ADA collected will be stored. Analysis will be performed only if required. If ongoing PK and/or ADA sampling is deemed to be unnecessary by the Sponsor, it may be reduced or discontinued.

### **8.6.1 Blood Collection for Serum MK-3475**

Sample collection, storage and shipment instructions for serum samples will be provided in the operations/laboratory manual.

## **8.7 Pharmacodynamics**

Sample collection, storage and shipment instructions for pharmacodynamic samples will be provided in the Procedure Manual.

## **8.8 Biomarkers**

To identify novel biomarkers, the following biospecimens to support exploratory analyses of cellular components (eg, protein, RNA, DNA, metabolites) and other circulating molecules will be collected from all participants in this study as specified in the SoA:

- Blood for Genetic Analysis
- Blood for RNA Analysis
- Blood for Plasma Biomarker Analysis
- Blood for Serum Biomarker Analysis
- Stool for Biomarker Analysis

- Blood for circulating tumor DNA (ctDNA)
- Tumor tissue

Sample collection, storage and shipment instructions for the exploratory biomarker specimens will be provided in the laboratory manual.

The sample for genetic analysis should be drawn for planned exploratory biomarker research. This sample will not be collected at the site if there is either a local law or regulation prohibiting collection, or if the IRB/IEC does not approve the collection of the sample for these purposes. If leftover extracted DNA will be stored for future biomedical research if the participant provides documented informed consent/assent for future biomedical research. If the genetic sample collection is not approved, but future biomedical research is approved and consent/assent is given, this sample will be collected for the purpose of future biomedical research.

